Predictive modeling—using elastic net regression models—will assess the ability of the cognitive measures to predict both initial intelligibility and intelligibility improvement. Model-specific hyper-parameters will be selected based on 10-fold cross-validation. Predictive models will be run separately for each speaker condition. For each speaker, two model specifications will be used: 1) main effects only and 2) main effects and all two-way interactions. The model predictions and variable importance metrics, as well as post hoc assessment of predictions, will inform on the nature of the important interactions. Predictive accuracy includes the root mean squared error (RMSE) and R^2 values for the cross-validated predictions. Variable importance will be extracted from each model using a permutation method wherein each variable is randomly permuted, and the difference in predictive accuracy between the observed variable and its randomly permuted counterpart was derived.

All analyses will be completed in the R statistical environment version 4.2.0 or higher.

Older Listeners

Transcript Analysis.

Listener transcriptions from both the pretest and posttest phases will be evaluated for accuracy using Autoscore, an open-source computer-based tool for automated intelligibility scoring (<http://autoscore.usu.edu>; Borrie et al., 2019). The Autoscore settings were calibrated to score a word as accurately transcribed, not only when it matched the target word but also when variations were due to tense changes or pluralization. Additionally, homophonic errors and prevalent spelling mistakes were scored as accurate utilizing a built-in list of commonly misspelled words. Each listener's performance was quantified by calculating the percentage of words correctly transcribed (PWC) in both testing phases, yielding a pretest PWC score and a posttest PWC score for each listener. These PWC scores were used to quantify initial intelligibility (pretest PWC) and intelligibility improvement (posttest PWC after accounting for pretest PWC).

Statistical Analysis.

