Initial analyses of the data will include descriptive statistics for the variables of interest, testing for differences in listener cognition between the speaker conditions, testing for average intelligibility improvement between pretest and posttest for the speakers, and calculating correlations between all variables of interest. First, descriptive statistics for listener age and cognitive scores will be calculated for the speaker conditions to ensure that the listeners assigned to each condition are equal. Differences in these variables between the speaker conditions will be tested using the Wilcoxon Rank Sum test since the data did not meet statistical assumptions for parametric testing. Descriptive statistics for pretest and posttest PWC scores for both speaker conditions will also be calculated. Intelligibility improvement between the pretest and posttest will be evaluated for each speaker condition using repeated-measures ANOVA with Cohen's d effect size estimates to test for significant and meaningful intelligibility change due to the perceptual training. Pearson correlation coefficient analyses will be conducted for each speaker condition to assess the correlation between the variables of interest (e.g., cognitive scores, intelligibility).

Elastic net regression models will be used to assess how well the cognitive measures and hearing acuity predict initial intelligibility and intelligibility improvement. Separate elastic net models will be run for each speaker condition as well as for each speaker for initial intelligibility and intelligibility improvement. Therefore, a total of four elastic net models will run during this analysis. Specification of the model includes all main effects as well as all two-way interactions between the variables. The elastic net models will be evaluated using the model accuracy and variable importance metrics. Post hoc assessments will also be conducted to evaluate the nature of the important main effects and interactions. Root mean squared error (RMSE) and R² will be used to evaluate the predictive accuracy of the cross-validated predictions to incentivize the model to find the predictive relationships that will likely generalize to untrained data. Variable importance will be extracted from each model using permutation. The main effects and interactions selected as important will be assessed via visual analysis of scatterplots depicting the prediction stratified by the variables in the interaction.

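### The planned plots of predictions describe a fitted interaction but are not evidence that it is real, and the older-listener plan has no interaction-specific check

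*Combined protocol and SAP*

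**What the plan says.** In the Older Listeners part of the SAP, under Statistical Analysis, each elastic net is specified in full: "Specification of the model includes all main effects as well as all two-way interactions between the variables". Accuracy is judged on cross-validated predictions: "Root mean squared error (RMSE) and R² will be used to evaluate the predictive accuracy of the cross-validated predictions". Terms are ranked by permutation: "Variable importance will be extracted from each model using permutation". No importance cut-off is given, and the text does not say whether importance is computed on held-out data.

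The follow-up step has a stated purpose: "Post hoc assessments will also be conducted to evaluate the nature of the important main effects and interactions". Its method is that terms selected as important are "assessed via visual analysis of scatterplots depicting the prediction stratified by the variables in the interaction". The text does not say whether the predictions are in-sample or out-of-fold. It mentions neither observed scores nor any measure of uncertainty in the plot.

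In the Younger Listeners part, under Statistical Analyses, the predictions and importance metrics, "as well as post hoc assessment of predictions, will inform on the nature of the important interactions". No scatterplots are mentioned there. That part does plan a comparison: "two model specifications will be used: 1) main effects only and 2) main effects and all two-way interactions". The older-listener part has no main-effects-only model.

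**The concern.** A fitted elastic net prediction is a fixed function of the listener's scores. If the net keeps a product term, predictions stratified by one of the two variables will generally have different slopes against the other. The net may have kept that term because the interaction exists or because of chance in these listeners, and the plot looks much the same either way. It also leaves out the listener-to-listener variation in the percentage of words correct (PWC) that would show how firmly the data support the pattern.

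For older listeners this plot is the last planned step before an interaction is interpreted, and nothing else in that part tests whether a selected interaction adds anything. Cross-validated RMSE and R² can look respectable on the strength of real main effects alone. The risk is that a chance interaction between, say, hearing and working memory is reported as a finding because the plotted slopes diverge.

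**Working it through.** **Counts from the documents.** Older listeners: 2 speaker conditions × 2 outcomes = 4 models, which reproduces the plan's figure of four. Predictors: 5 cognitive measures + hearing = 6. Two-way interactions: 6 × 5 / 2 = 15, so 6 + 15 = 21 terms per model. If pretest PWC also enters, 7 predictors give 21 interactions and 28 terms; with age as well, 8 give 28 and 36.

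**Simulation assumptions (none is in the documents).** Six predictors with pairwise correlation 0.3; true main effects 1, 1 and 0.5 per SD on three of them; no true interaction; true R² = 0.3; elastic net mixing value 0.5; penalty chosen by 10-fold cross-validation; n per condition 40, 80 or 150, with 200, 250 and 250 runs.

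**Measure.** For the largest interaction kept, which is false by design, take the slope of the plotted quantity on the first variable in the upper half of the second variable, minus the same slope in the lower half. Ask whether the difference has the sign of the fitted coefficient.

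| | n = 40 | n = 80 | n = 150 |
|---|---|---|---|
| Runs keeping at least one false interaction | 87% | 93% | 98% |
| Median number kept in those runs | 5 | 5 | 4 |
| Shown in fitted direction: fitted predictions | 94% | 94% | 92% |
| Same: out-of-fold predictions | 84% | 93% | 91% |
| Same: observed scores, same listeners | 95% | 98% | 96% |
| Same: observed scores, new listeners | 50% | 48% | 49% |
| Mean slope difference, fitted predictions | 0.73 | 0.54 | 0.39 |
| Mean slope difference, new listeners | 0.02 | -0.03 | -0.03 |
| Mean cross-validated R² in those runs | 0.16 | 0.20 | 0.25 |

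The smallest base for the direction percentages is 0.865 × 200 = 173 runs, so the standard error of the 50% entry is √(0.5 × 0.5 / 173) = 3.8 percentage points.

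**Reading.** The fitted plot shows slope differences of 0.39 to 0.73, against true main-effect slopes of 1, 1 and 0.5, where the truth is zero. The cross-validated R² of 0.16 to 0.25 comes with real main effects and does not flag the false interaction.

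**Would observed data help?** Direction alone does not: the same listeners agree in 95% to 98% of runs, because the term was selected on their data. A measure of uncertainty helps in part:
- With n = 50 assumed and no true interaction, observed scores agreed in direction in 97% of runs. A 95% bootstrap band on the observed slope difference supported the false interaction in only 21% (raw PWC) or 38% (partial residuals).
- In a separate run with partial residuals by tertile, the band supported 100 − 57 = 43% of false interactions at n = 50 and 100 − 53 = 47% at n = 80. It supported 65% and 80% of true ones that were kept (assumed coefficient 0.35).

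A 95% band should support a null difference about 5% of the time. Rates of 21% to 47% show that the effect of selection remains.

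**The case against.** The strongest answer is that the plot is not meant as a test. Both parts of the SAP say it is there to describe the form of effects already selected, and plotting predictions is an ordinary way to do that. Protection against overfitting is left to shrinkage, cross-validated accuracy and permutation importance, and younger listeners also have a main-effects-only model. This stands. It is why the point is a missing check and a labelling matter, and not a faulty method.

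A reader might infer more than the documents support:
- *That the plot is the only evaluation planned.* It is not. Accuracy and importance are evaluated too, although for older listeners neither is stated in a way that tests a particular interaction.
- *That the plot must, by construction, confirm every false interaction.* The other predictors also move the predictions, and agreement was 92% to 94%, not 100%. The plan also leaves open whether predictions are out-of-fold (84% to 93%) and whether observed points are drawn.
- *That the number of non-zero false interactions, about 3 to 5 per model in simulation, is the number that would be plotted.* The plan plots only terms selected as important, and the importance step was not simulated.
- *That replacing predictions with observed scores would settle the matter.* The 95% to 98% agreement in the same listeners shows that it would not.

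**Conclusion.** The point holds in a limited form. The prediction plot describes the fitted interaction and is not independent evidence for it. The older-listener plan contains nothing else that tests whether a selected interaction is real. The younger-listener plan is better placed because its two specifications allow the gain from interactions to be seen.

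Under the assumed settings, fitted plots displayed the largest false interaction about nine times in ten, against about five in ten in new listeners. The size depends on the assumed n, R², correlation and mixing value, and on taking the largest non-zero interaction as the one plotted. The reasoning does not depend on those values. Severity is minor: this is a cheap improvement to how interactions are reported, and the documents do not support calling the plot a failed confirmatory test.

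**What to change.** Keep the prediction plots and amend the SAP along these lines:

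1. In both cohorts, label the plots descriptive and state whether the predictions are in-sample or out-of-fold.
2. Overlay observed PWC. For improvement, use partial residuals given pretest PWC and the other terms.
3. Report the slope difference between strata with a bootstrap interval that repeats the whole elastic net selection, including tuning, in each resample. Also report how often the interaction is kept. The performance of an interval that repeats selection has not been established here, so it should be read as a measure of stability and not as a formal test.
4. For older listeners, add the main-effects-only model already planned for younger listeners, and report the difference in cross-validated RMSE and R² between the two specifications.
5. State that visual agreement in the same listeners is not taken as proof of an interaction, because the term was selected on those data.

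The cost is noisier plots, a few SAP sentences and a little more computation. Item 4 raises the older-listener count from 4 to 2 conditions × 2 outcomes × 2 specifications = 8 models, so the stated total needs updating. No new data are needed.
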